8.4.7 Pharmacokinetic Endpoints

The PK Analysis Set will be used for PK analyses.

Plasma concentrations of setanaxib and GKT138184, along with blood sampling dates and actual blood sampling time relative to dosing time, will be listed by dose group, patient, and nominal sampling time. Pre-dose and post-dose plasma concentrations of setanaxib and GKT138184 will be summarised as appropriate. AUC(0-24)-ss, Cmin-ss and Cmax-ss will be estimated for each individual patient using non-linear mixed effect methodology and prior PK knowledge of the compound, and summarised as appropriate. More details regarding the PK analysis and exploratory PK/PD analyses will be provided in a separate pharmacokinetic analysis plan.

An interim pharmacokinetic analysis will be performed at the initial data cut-off approximately 9 weeks after completion of enrolment, when all patients are expected to have had at least 3 cycles of pembrolizumab, at least one post-treatment scan, and the opportunity for a post-treatment tumour biopsy. This analysis will result in an interim report.

The final pharmacokinetic analysis will be performed at the end of the study after database lock. If the predicted timing of the initial and final analyses are expected to be close in proximity, only one analysis may be performed. Only the final analysis will be reported formally and summarised for the CSR.

8.4.8 Handling of Missing Values

Rules for imputation of missing data will be detailed in the SAP.

9 ETHICS AND RESPONSIBILITIES

9.1 Good Clinical Practice

This study will be conducted in accordance with the Note for Guidance on ICH guidelines on GCP Harmonised Tripartite Guideline E6 (R1)/Integrated Addendum E6 (R2); United States Food and Drug Administration (US FDA) Code of Federal Regulations (Title 21 Parts 50, 56, 312), requirements for the conduct of clinical studies as provided in the European Directive 2001/20/EC; the general guidelines indicated in the Declaration of Helsinki; and all applicable regulatory requirements.

9.2 Institutional Review Board/Independent Ethics Committee

Before initiating a study, the investigator/institution must have written and dated approval/favourable opinion from the IRBs/IECs for the study protocol/amendment(s), written ICF, any ICF updates, patient recruitment procedures (eg, advertisements), and any written information to be provided to patients and a statement from the IRBs/IECs that these comply with GCP requirements (if applicable). A current copy of the IB should be included as part of the written application to the IRB/IEC.

The IRB/IEC approval(s) must identify the protocol version as well as the documents reviewed. Any amendments to the protocol will require IRB/IEC approval before the implementation of the changes made to the study, except for changes necessary to eliminate an immediate hazard to the study patients.

The investigator will be responsible for the following:

- Providing written summaries of the status of the study to the IRB/IEC annually or more frequently in accordance with the requirements, policies, and procedures established by the IRB/IEC
- Notifying the IRB/IEC of SAEs or other significant safety findings, including adverse drug reactions that are both serious and unexpected, as required by IRB/IEC procedures
- Providing oversight of the conduct of the study at the site and adherence to the requirements of all applicable regulations
- Promptly reporting deviations from, or changes to, the protocol to eliminate immediate hazards to the study patients

9.3 Informed Consent

In obtaining and documenting informed consent, the investigator should comply with the applicable regulatory requirement(s) and should adhere to GCP and to the ethical

principles that have their origin in the Declaration of Helsinki. Prior to the beginning of the study, the investigator should have the IRB/IEC's written approval/favourable opinion of the written ICF and any other written information to be provided to study patients.

- The investigator or his/her representative will explain the purpose and nature of the study as well as possible AEs to the patient or his/her legally acceptable representative and answer all questions regarding the study.
- Patients must be informed that their participation is voluntary, and consent can be withdrawn at any point.
- Patients or their legally acceptable representative will be required to sign a statement of informed consent that meets the requirements of local regulations, ICH guidelines, and the IRB/IEC or study site.
- Prior to a patient's participation in the study, the written ICF should be signed and personally dated by the patient or by the patient's legally acceptable representative, and by the person who conducted the informed consent discussion.
- The medical record must include a study identifier and a statement that written informed consent was obtained before the patient was enrolled in the study and the date the written consent was obtained.
- The original copy of the signed ICF will be retained at the study site.
- A copy of the ICF and any other written information must be provided to the patient or the patient's legally acceptable representative.
- If the ICF is revised, the revised ICF must have received the IRB/IEC's approval/favourable opinion in advance of its use. Patients must be informed of the changes to the ICF and must re-consent to the most current version during their participation in the study. The patient or the patient's legally acceptable representative should be informed in a timely manner if new information becomes available that may be relevant to the patient's willingness to continue participation in the study. The communication of this information should be documented.

A patient who is rescreened is not required to sign another ICF if the rescreening occurs within 35 days of the previous ICF signature date.

The ICF will contain a separate section that addresses the collection of a third optional tumour biopsy for an additional assessment of tumour biomarkers and gene expression analysis. The investigator (or authorised designee) will explain to each patient the objectives of this research. Patients will be told that they are free to refuse to participate and may withdraw their consent at any time and for any reason.

If a patient is unable to read or if a legally acceptable representative is unable to read, an impartial witness should be present during the entire informed consent discussion. The witness should sign and personally date the ICF after:

- The written ICF and any other written information to be provided to patients is read and explained to the patient or the patient's legally acceptable representative
- The patient or the patient's legally acceptable representative has orally consented to the patient's participation in the study
- The patient or the patient's legally acceptable representative has signed and personally dated the ICF, if they are capable of doing so

By signing the ICF, the witness attests that the information in the ICF and any other written information was accurately explained to, and apparently understood by, the patient or the patient's legally acceptable representative, and that informed consent was freely given by the patient or the patient's legally acceptable representative.

9.4 Independent Data Monitoring Committee

The IDMC will oversee the safety of participating patients.

Treatment safety and tolerability will be regularly reviewed, with the first assessment after approximately 12 patients (6 per treatment group) have had the opportunity to complete at least 1 cycle of pembrolizumab +/- setanaxib, followed by periodic assessments at a frequency defined in the IDMC Charter.

The IDMC may recommend change(s) to the setanaxib dose regimen or study conduct based on the safety data reviews, as defined in the IDMC Charter. The IDMC will include an unblinded statistician and 2 physicians (one of whom shall have expertise in head and neck cancer), and will be supported by an IDMC Specialist and programmers, as well as any other functions detailed in the IDMC Charter.

The role and responsibilities of the IDMC will be outlined in the IDMC Charter.

9.5 Financing and Insurance

9.5.1 Contractual and Financial Details

The investigator (and/or, as appropriate, the hospital administrative representative) and the CRO and/or sponsor (or designee) will sign a clinical trial agreement prior to the start of the study, outlining overall sponsor and investigator responsibilities in relation to the study. The contract should describe whether costs for pharmacy, laboratory, and other protocol-required services are being paid directly or indirectly.
9.5.2 Insurance, Indemnity, and Compensation

The sponsor will maintain an appropriate clinical study insurance policy.

9.5.3 Financial Disclosure

Investigators and sub-investigators will provide the sponsor with sufficient, accurate financial information as requested to allow the sponsor to submit complete and accurate financial certification or disclosure statements to the appropriate regulatory authorities.

10 RECORDS MANAGEMENT

All clinical study information should be recorded, handled, and stored in a way that allows its accurate reporting, interpretation, and verification. This principle applies to all records referenced in this protocol, irrespective of the type of media used.

An eCRF will be used to store and transmit patient information. Information from the medical records (progress notes) and other source documents is to be promptly entered into the appropriate section of the eCRF. The eCRF must be reviewed and electronically signed and dated by the investigator on an ongoing basis. The investigator is responsible for verifying that the data entries are accurate and correct by signing the eCRF.

Access to the eCRF will be strictly password protected and limited to personnel directly participating in the study. Data should be entered into the eCRF completely by authorised site personnel (eg, investigators and the study coordinator). The eCRF must be completed as soon as possible after any patient evaluation or communication. If data are to be changed due to erroneous input or other reason, an electronic audit trail will track these changes. The eCRFs and computers that store them must be accessible to study monitors and other regulatory auditors.

During each study visit, a physician participating in the study will maintain progress notes in the patient's medical records to document all significant observations. At a minimum, these notes are to contain:

- The date of the visit and the corresponding day or visit in the study schedule
- General condition and status remarks by the patient, including any significant medical findings. The severity, frequency, duration, and resolution of any reported AE, and the investigator's assessment as to whether or not the reported AE is related to IMP
- Changes (including dosages) in concomitant medications/therapies (including medical foods) or procedures
- A general reference to the procedures completed
- Protocol deviations identified that could potentially affect safety and/or study results
- The signature or initials of all physicians making an entry in the medical record (progress notes)

In addition, any contact with the patient via telephone or other means that provides significant clinical information is to also be documented in the medical record (progress notes), as described above.

Changes to information in the medical record (progress notes) and other source documents are to be initialled and dated on the day the change is made by the investigator (or designee). If the reason for the change is not apparent, a brief explanation for the change is to be written adjacent to the change. Changes to the eCRF will be electronically tracked.

A data management plan will be written and finalised prior to performing any data validation.

10.1 Source Documentation

Source documents contain the results of original observations and activities of a clinical investigation. They are the original records in which raw data are first recorded. Source documents include, but are not limited to, medical records (progress notes), ECG and computer printouts, screening logs, completed scales, QoL questionnaires, and recorded data from automated instruments.

The investigator/site personnel should maintain adequate and accurate source documents and study records that include all pertinent observations on each of the site's study patients. Source data should be attributable, legible, contemporaneous, original, accurate, and complete. Changes to source data should be traceable, should not obscure the original entry, and should be explained if necessary (eg, via an audit trail).

All source documents from this study are to be maintained by the investigator and made available for inspection by authorised persons. The investigator will provide direct access to source documents/data for study-related monitoring, audits, IRB/IEC review, and regulatory inspections. The sponsor should verify that each patient has consented, in writing, to direct access to his/her original medical records for study-related monitoring, audit, IRB/IEC review, and regulatory inspection.

10.2 Electronic Case Report Form Completion and Data Management

An eCRF will be used to store and transmit patient information. The file structure and format for the eCRF will be provided by the sponsor or its representative and should be handled in accordance with the instructions provided.

The eCRF must be reviewed and electronically signed and dated by the investigator.

Access to the eCRF will be strictly password protected and limited to personnel directly participating in the study. Data should be entered into the eCRF completely by authorised site personnel (eg, investigators and the study coordinator). The eCRF must be completed as soon as possible after any patient evaluation or communication. If data are to be changed due to erroneous input or other reason, an electronic audit trail will track the changes. The eCRFs and computers that store them must be accessible to study monitors and other regulatory auditors. Changes to the eCRF will be electronically tracked.

Data will be entered/loaded into a validated electronic database using a clinical data management system. Computerised data cleaning checks will be used in addition to manual review to check for discrepancies and to ensure consistency of the data.

10.3 Study Files and Record Retention

All data derived from the study will remain the property of the sponsor. The sponsor assumes accountability for actions delegated to other individuals, eg, the CRO.

Records must be retained in accordance with the current ICH guidelines on GCP. All essential study documents, including records of patients, source documents, eCRFs, and the IMP inventory, must be kept on file.

Essential documents should be retained until at least 2 years after the last approval of a marketing application in an ICH region and until there are no pending or contemplated marketing applications in an ICH region, or until at least 2 years have elapsed since the formal discontinuation of clinical development of setanaxib. However, essential documents may be retained for a longer period if required by the applicable regulatory requirements or by agreement with the sponsor. The sponsor is responsible for informing the investigator when these documents need no longer be retained.

The investigator is not to dispose of any records relevant to this study without written permission from the sponsor and is to provide the sponsor the opportunity to collect such records. The investigator shall take responsibility for maintaining adequate and accurate hard copy source documents of all observations and data generated during this study. Such documentation is subject to inspection by the sponsor, its representatives, and regulatory authorities.

If an investigator moves, withdraws from a study, or retires, the responsibility for maintaining the records may be transferred to another person who will accept responsibility. Notice of transfer must be made to and agreed by the sponsor.

11 AUDITING AND MONITORING

Sponsor-assigned monitors will conduct regular site visits to the investigational facilities for the purpose of monitoring various aspects of the study, such as verifying that the ICFs were signed and dated before any study-specific procedure was performed, assessing patient enrolment, compliance with protocol procedures, completeness and accuracy of data entered into the eCRFs, verification of eCRF data against original source documents, and occurrence of AEs. The investigator must agree to sponsor-authorised personnel having direct access to the clinical (or associated) files and clinical study supplies (dispensing and storage areas) to ensure compliance with applicable regulations, and the investigator will assist with the sponsor's monitoring activities.

Quality control will occur at each stage of data handling to ensure that all data are reliable and have been processed correctly. The sponsor should ensure oversight of any study-related duties and functions carried out on its behalf, including study-related duties and functions that are subcontracted to another party by the sponsor's contracted CRO(s).

The eCRFs should be completed in a timely manner and on an ongoing basis to allow regular review by the study monitor.

Details describing the strategy, responsibilities, and requirements of study monitoring are provided in the study Monitoring Plan.

The purpose of an audit is to assess whether ethics, regulatory, and quality requirements are being fulfilled. The sponsor or its representative may conduct audits at the investigative sites including, but not limited to, drug supply, presence of required documents, the informed consent process, and comparison of eCRFs with source documents. Government regulatory authorities may also inspect the investigator during or after the study. The investigator (or designee) should contact the sponsor/CRO immediately if this occurs. All medical records (progress notes) must be available for audit. The investigator must agree to participate with audits conducted at a convenient time in a reasonable manner.

11.1 Risk and Quality Tolerance Limits

Perceived risks and quality tolerance limits (QTLs) will be identified and documented in the Protocol Risk Evaluation Plan before the start of the study.

The sponsor will review risk control measures periodically to ascertain whether the implemented quality management activities remain effective and relevant. The quality management approach and any important deviations from the predefined QTLs (and remedial actions adopted) will be described in the clinical study report (CSR).

11.2 Protocol Adherence and Deviations

The investigator and site personnel should conduct the study in compliance with the protocol and should use continuous vigilance to identify and report protocol deviations.

A protocol deviation is any change, divergence, or departure from the study design or procedures defined in the protocol that may be on the part of the investigator, site personnel, or the patient.

Important protocol deviations are a subset of protocol deviations that may significantly impact the completeness, accuracy, and/or reliability of the study data or that may significantly affect a patient's rights, safety, or well-being. For example, important protocol deviations may include enrolling patients in violation of key eligibility criteria designed to ensure a specific patient population or failing to collect data necessary to interpret primary endpoints, as this may compromise the scientific value of the study.

The investigator should not implement any deviation from the protocol without agreement from the sponsor and prior review and approval from the IRB/IEC of an amendment, except where necessary to eliminate an immediate hazard to a study patient, or when the change involves only logistical or administrative aspects of the study, such as a change in a monitor or telephone number.

In the event of an important protocol deviation, the investigator will discuss the deviation with the sponsor's medical monitor and will come to an agreement as to whether the patient should be withdrawn from the study due to the important protocol deviation.

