4.3.2 Premature Discontinuation from the Study

Participation in the study is strictly voluntary. A patient has the right to withdraw from the study at any time for any reason, without any reprisal.

The investigator has the right to terminate participation of a patient for any of the following reasons:

- Violation of the protocol jeopardising patient safety and/or integrity of study results
- Any other reason relating to the patient's safety
- Any other reason relating to the integrity of the study data

Investigators should make every effort to discuss with the study monitor/sponsor before discontinuing a patient from the study.

If a patient is withdrawn from the study, the study monitor/sponsor will be informed immediately. If there is a medical reason for withdrawal, the patient will remain under the supervision of the investigator until satisfactory health has returned.

If the patient withdraws consent for disclosure of further information, the sponsor may retain and continue to use any collected data before such a withdrawal of consent. If a patient withdraws from the study, he/she may request destruction of any samples taken and not tested, and the investigator must document this in the site study records.

Although a patient is not obliged to give his/her reason(s) for withdrawing prematurely from a study, the investigator should make a reasonable effort to ascertain the reason(s), while fully respecting the patient's rights.

At the time of premature study discontinuation, the investigator should make every effort to ensure the patient completes the assessments indicated at the EoT Visit (see Table 1).

Patients who prematurely discontinue from the study cannot subsequently re-join the study.

For details on the discontinuation of study sites or the study as a whole, see Section 14.

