- Intercurrent events: premature study discontinuation, study drug interruption/premature discontinuation, use of certain alternative or additional therapy including a new anti-cancer therapy

The PFS follow-up will continue to objective progression regardless of the stated intercurrent events. Patients who withdraw completely from the study will be right-censored. For the patients who are right-censored, the time until which they were in the study from the randomisation would be recorded as the right-censored time. The treatment policy strategy used addresses the intercurrent events listed above. The occurrence of the intercurrent event in this case is considered irrelevant in defining the

treatment effect of interest: the value for the variable of interest is used regardless of whether or not the intercurrent events occur. For example, when specifying how to address use of additional anti-cancer therapy prior to disease progression as an intercurrent event, the values of the variable of interest will be used whether or not the patient takes the additional anti-cancer therapy. In the case of premature study discontinuation, and whether or not a patient experiences changes in other treatments (eg, background or concomitant treatments), the intercurrent event will be considered to be part of the treatments being compared. In that case, this reflects the comparison under the usual intent-to-treat principle as the effect of a treatment policy.

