For studies where the response rate is the primary endpoint it is strongly recommended that all responses be reviewed by an expert(s) independent of the study at the study's completion. Simultaneous review of the patients' files and radiological images is the best approach.

Reporting of results

All patients included in the study must be assessed for response to treatment, even if there are major protocol treatment deviations or if they are ineligible.

All of the patients who met the eligibility criteria should be included in the main analysis of the response rate.

All conclusions should be based on all eligible patients.

Sub-analyses may then be performed on the basis of a subset of patients, excluding those for whom major protocol deviations have been identified (eg, early death due to other reasons, early discontinuation of treatment, major protocol violations, etc). However, these sub-analyses may not serve as the basis for drawing conclusions concerning treatment efficacy, and the reasons for excluding patients from the analysis should be clearly reported.

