10.7.6 Best Percentage Change for Primary Endpoint

Best percentage change from baseline in tumour size will be derived as the largest percentage decrease or the smallest percentage increase in tumour size from baseline.

In order to account for intercurrent events;

- Only values prior to the occurrence of premature study discontinuation or the use of alternative or additional therapy including a new anti-cancer therapy will be considered.
- Where a patient prematurely discontinues treatment, all values will be considered up to the point of PD.
- Where a patient has no evaluable post-baseline assessments, but presents evidence of either death or PD, a value of 20% will be imputed as the best percentage change from baseline. If a log transformation is required for analysis, a value of 0.182321557 will be imputed as the ratio of log(best postbaseline) to log(baseline), which represents a 20% increase when back transformed to the original scale (exp[0.182321557]=1.2).

Note that the BOR in these instances should also be imputed as PD (see Section 10.9.2).

Patients whose data have been imputed will be flagged in listings and waterfall plots where appropriate.

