10.8 Survival

10.8.1 Progression Free Survival

The definition of PFS is the time from randomisation to the first documented disease progression per RECIST v1.1 or death due to any cause, whichever occurs first. This is calculated as:

PFS(days) = (Date of (PD or Censoring) - Date of Randomization) + 1

The event time for PFS will be censored on the date of randomisation with duration of 1 day for;

 Patients lacking any evaluation of disease after first study treatment (unless, they die within 2 scheduled tumour assessments of baseline, this will be treated as an event with the date of death as the event date).

The event time for PFS will be censored at the date of the last available assessment documenting absence of PD for the following scenarios;

- Patients who prematurely discontinue from the study.
- Any PD that occurs immediately after two consecutive missed visits.
- Patients who receive subsequent systemic anti-cancer therapy.
- Patients who are alive and progression-free at the time of a data cut off or End of Study.

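### Protocol 11.2 and 4.3.2 let a protocol deviation end study participation, and with it outcome follow-up, in conflict with Section 4.3.1 and Appendix IV

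*Protocol*

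**What the plan says.** **Provisions that end participation**

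- Protocol 11.2: after an important deviation the investigator and the medical monitor "will come to an agreement as to whether the patient should be withdrawn from the study due to the important protocol deviation". The same section gives as an example that "important protocol deviations may include enrolling patients in violation of key eligibility criteria"; its other example is failure to collect data needed for the primary endpoint.
- Protocol 4.3.2: the investigator may terminate participation on several grounds. One is "Violation of the protocol jeopardising patient safety and/or integrity of study results", and another is any other reason concerning data integrity. The exit is final: "Patients who prematurely discontinue from the study cannot subsequently re-join the study".

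**Provisions that keep follow-up going**

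- Protocol 4.3.1: noncompliance is a reason to stop IMP. Patients who stop treatment before radiological progression are still followed for tumour assessment to RECIST progression and for survival.
- Protocol 4.3.1, closing paragraph: for a patient started on treatment in error despite failing eligibility, the question to be discussed is whether treatment continues.
- Protocol Appendix IV: "All patients included in the study must be assessed for response to treatment, even if there are major protocol treatment deviations", and the sentence goes on to include ineligible patients.

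**Analysis rules that apply after study discontinuation**

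- SAP 10.7.6, best percentage change: "Only values prior to the occurrence of premature study discontinuation", or before a new therapy, are considered.
- SAP 10.8.1, PFS: the groups censored at the last progression-free assessment include "Patients who prematurely discontinue from the study".

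**The concern.** Deviations such as missed doses, a prohibited drug or a missed scan happen after randomisation and may be related to tolerability or to how the patient is doing. If a deviation ends study participation, an adherence or conduct problem becomes missing outcome data, possibly informative, in the full analysis set (FAS). The exit is irreversible, so one missed scan could lead to the loss of all later ones.

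The plan has little to detect or repair this. SAP 12.5.2.3 plans no sensitivity analysis of the primary endpoint, and SAP 12.5.2.1 rules out further imputation methods. The repeat on the Per-Protocol Analysis Set (PPS) excludes patients flagged for a deviation affecting the primary endpoint (SAP 9.2.4), so it cannot restore their data.

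**Working it through.** **1. The provisions side by side**

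| Trigger | Protocol 11.2 / 4.3.2 | Elsewhere in the protocol |
|---|---|---|
| Noncompliance affecting the results | Study withdrawal possible | 4.3.1: IMP stopped, scans and survival follow-up continue |
| Eligibility violation | Important deviation, study withdrawal possible | 4.3.1, closing paragraph: decision about treatment only |
| Major deviation or ineligibility | Study withdrawal possible | Appendix IV: patient still assessed for response |

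The first two rows give two consequences for the same event. The third sets a discretionary exit against a requirement to assess everyone.

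**2. What data are lost**

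- The patient stays in the FAS (Protocol 8.2, SAP 9.2.3), and values before withdrawal are used.
- SAP 10.7.6 imputes a 20% increase only when there is no evaluable post-baseline assessment and there is evidence of progression or death. A patient withdrawn before the first evaluable scan without either has no primary value.
- Protocol 4.3.1 offers continued survival contact to patients who withdraw consent. No equivalent route is given for a patient withdrawn by the investigator or the medical monitor. Yet the OS estimand in SAP 9.1.2 uses outcomes regardless of every intercurrent event except study completion or data cut-off.

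**3. The plan's own figures (Protocol 8.3)**

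Inputs: 25 per arm, difference 20, SD 30, two-sided alpha 0.20. For PFS: hazard ratio 0.5, 38 events, two-sided p<0.2.

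- Primary: noncentrality = 20 / (30 × √(2/25)) = 2.357 on 48 degrees of freedom. The noncentral t distribution gives power 85.4%; the plan states 85%.
- PFS (Schoenfeld): Φ(√38/2 × ln 2 − 1.2816) = Φ(2.1364 − 1.2816) = Φ(0.855) = 0.8037; the plan states more than 80%.

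Both reproduce.

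**4. Illustration of loss**

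The documents give no rate of deviation-based withdrawal, so the losses below are assumptions.

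| Usable values lost per arm | n per arm | Noncentrality 20 / (30√(2/n)) | Power |
|---|---|---|---|
| 0 | 25 | 2.357 | 85.4% |
| 1 | 24 | 2.309 | 84.3% |
| 2 | 23 | 2.261 | 83.1% |
| 3 | 22 | 2.211 | 81.8% |

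*Selective loss.* If k of 25 patients in one arm are lost and their mean outcome lies m SDs from the arm mean, that arm's mean shifts by k × m × 30 / (25 − k). For k = 2, this is 2 × 0.5 × 30 / 23 = 1.3 points at m = 0.5 and 2 × 1 × 30 / 23 = 2.6 points at m = 1, against a 20-point target.

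*PFS.* Protocol 3.1 continues follow-up until at least 38 progression events. With 50 patients, 50 − 38 = 12 can remain without an event and the target is still reached, so a few censored patients mostly postpone the analysis. Only if the count were not made up would power fall: the same formula gives 0.7875 with 36 events and 0.7701 with 34.

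**The case against.** The case on the other side has real force on several points.

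- **Section 3.1 is not literally contradicted.** It continues scans whatever happens to treatment and does not address leaving the study, which has its own section. The conflict there is one of intent. Section 5.2.1.2 also lets imaging end when the sponsor notifies the site, which could cover an agreed withdrawal.
- **PFS censoring agrees with the protocol.** A reader might infer from the treatment-policy sentence in Protocol 8.4.2 ("the value for the variable of interest is used regardless of whether or not the intercurrent events occur") that SAP 10.8.1 departs from it. The same section right-censors patients who withdraw completely, so it does not. The SAP's hybrid strategy for the primary endpoint is a declared change (SAP 6.1.1) and a separate matter.
- **Appendix IV is a summary of general RECIST guidance.** The sentence sits under reporting of results and can be read as saying who counts in the response analysis. Withdrawn patients do stay in the FAS. Even so, it names deviations and ineligibility, and it is hard to square with ending assessment because of them.
- **Withdrawal is discretionary and the staff are blinded** (Protocol 6.2). This limits selection by arm but does not prevent data loss.
- **Specific rules already cover most examples.** Noncompliance and prohibited medication have IMP rules in 4.3.1. That supports reconciling the text, because 11.2 does not say that those rules take precedence.
- **Ending participation can be justified.** Section 11.2 includes deviations that affect a patient's rights, safety or well-being. A reader might infer that study withdrawal should be confined to consent withdrawal, loss to follow-up and death. The documents do not support going that far, because 4.3.2 has a separate patient-safety ground that is not in question here.

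The conflicts with both parts of Section 4.3.1 survive these points, and so does the tension with Appendix IV.

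**Conclusion.** The point holds as an internal inconsistency that can lose outcome data. Sections 11.2 and 4.3.2 permit irreversible study withdrawal for a deviation or for data integrity, where 4.3.1 and Appendix IV would keep the patient under assessment. The SAP rules then truncate best change and censor PFS.

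The size is unknown and probably modest. Losing 1 to 3 usable values per arm, an assumed range, costs about 1 to 4 percentage points of primary power (85.4% to between 84.3% and 81.8%). The selective-loss shifts of 1.3 to 2.6 points rest on assumed values of k and m.

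Two stronger inferences are not supported. One is that each withdrawal removes 1/38 = 2.6% of the PFS information: the event target is a minimum, so the main effect is delay. The other is that a particular share of patients will be lost this way: the documents give no rate, and up to 20 extra patients are allowed partly to offset early study discontinuation.

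The protocol supplied is v4.0 (25 April 2023), whereas the SAP was written against v5.0 (12 December 2023). The conclusion assumes that the relevant wording is unchanged in v5.0.

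**What to change.** First check Sections 11.2, 4.3.1 and 4.3.2 and Appendix IV in protocol v5.0. If the wording stands, reconcile them by stating that:

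1. a protocol deviation or data-integrity concern does not by itself end outcome follow-up;
2. scans to RECIST progression and survival contact continue for such patients unless they withdraw consent;
3. deviations are handled in the analysis through the existing flag that defines the PPS (SAP 9.2.4).

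Leave the patient-safety ground in 4.3.2 unchanged, and leave any decision about treatment to the protocol's existing clinical rules.

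The cost is a few sentences in an amendment and a memo to sites. The downside is some additional scans and contacts in patients who are off treatment, which Section 4.3.1 already expects of patients who stop treatment before progression.
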